Investigators primarily tested a participant-facing app to reduce opioid intake which was designed and implemented through a user-centered design approach. The intervention app provided education on elements of pain management that could be modified by patients, including: 1) post-operative pain expectations, 2) pharmacologic alternatives to opioids, 3) opioid safety and appropriate disposal, and 4) non-pharmacological therapy, such as meditation. The control app featured the same interface but only collected patient data. The app was deployed to research team members and pilot participants for beta testing before finalization.

Baseline information was obtained from the participant in-person during the index hospitalization. During this visit, patients familiarized themselves with the format, asked questions, and received explanations regarding the apps' functionality. Following discharge, a weekly notification was sent to the participant, reminding them to complete standardized surveys and custom questionnaires during the first four weeks following discharge, a time when most opioids are consumed and when patients have shown to report consumption accurately. The day of discharge was considered day 0. If no responses were obtained via the app, participants were followed up by telephone.

In addition to the participant-facing app intervention, a clinician-facing decision support tool was operationalized for the second half of the study period for participants not requiring opioids 24 hours prior to discharge. Previous work in three diverse samples of surgical procedures found that among available predictor variables that could be incorporated into an electronic decision support tool, 24-hour pre-discharge opioid intake was most strongly associated with patient-reported post-discharge opioid intake.

Outcomes

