The primary outcome was self-reported cumulative oral morphine milligram equivalents (MME) in the first four weeks after discharge. The secondary outcomes were amount of opioid prescription at discharge, supplementary opioid prescriptions within four weeks after discharge, disposal of leftover opioids within four weeks of discharge, pain intensity scores during the four weeks after discharge, and pain interference scores during the four weeks after discharge. Non-opioid prescriptions within four weeks of discharge were an exploratory outcome. Pain intensity and interference were both quantified using the National Institutes of Health Patient-Reported Outcomes Measurement Information System (PROMIS®) four-item pain intensity scale at four weeks and the four-item scale pain interference score at four weeks. All PROMIS™ scores were analyzed as standardized T-scores (mean 50, standard deviation 10).

Independent variables included sociodemographic characteristics obtained from the electronic health record and from a questionnaire provided to participants during their hospitalization: age, sex, race, ethnicity, body mass index (kg m²-1), and insurance type. Health history variables were obtained via surveys and electronic health records as necessary and included history of substance use disorder, PROMIS™ Sleep Disturbance Score, Patient Health Questionnaire-(PHQ-8) score, pre-operative opioid use, preoperative benzodiazepine use, preoperative gabapentinoid use, and preoperative antidepressant use. Clinical characteristics included the primary surgical subspecialty for the requisite hospital stay, multiple procedures performed during admission, total in-hospital opioid intake, pain score at discharge, and length of hospital stay.

Adverse events were monitored. For this study, an adverse event was considered as one requiring more than two additional opioid prescriptions within two weeks of discharge and/or access of confidential information by a non-authorized person. We considered a serious adverse event as all-cause mortality and/or re-hospitalization for any reason.

Statistical analysis

Baseline balance on potential confounding characteristics was assessed using absolute standardized difference (ASD), calculated as the difference in means or proportions divided by the pooled standard deviation. A variable was considered imbalanced if the ASD was greater than 0.16.

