For the primary analysis, the effect of the intervention app on self-reported cumulative opioid use in the four weeks after discharge was modeled by log-transforming the outcome variable and then fitting a linear regression model with the app treatment group as the covariate. The treatment effects were estimated as ratio of geometric means. A sensitivity analysis was conducted using quantile regression to test the robustness of results to outliers. A model was fit with an interaction between app and decision support tool groups to evaluate potential multiplicative effects between the groups. Analysis was on a modified intention-to-treat basis, excluding participants that did not engage with the intervention or answer survey questions. There were no partial responses to the opioid-related outcomes. Missing data from pain-related survey responses were imputed from the mixed effects model.

For the secondary analysis, the effect of the intervention app on opioids prescribed at discharge was modeled by log-transforming the outcome and fitting a linear regression model with the app treatment group as the covariate. The effect of the intervention app on supplementary opioid requirements in the four weeks after discharge, opioid disposal, and non- opioid prescriptions in the four weeks after discharge was evaluated using a logistic regression model. The effect of the app on pain intensity and interference t-scores was evaluated by fitting linear mixed models with fixed covariates for app treatment group and time (categorical), and random effects for participant identification code. No interim analyses were planned because the population studied was not considered high risk for adverse events, the interventions were generally considered not harmful and to prevent alpha dilution.

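### The adverse-event rule omits analgesic side effects and visits without admission, and no adverse-event analysis by arm is specified, so a low count cannot show that the app is safe

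*Combined protocol and SAP*

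**What the plan says.** The safety text in the Outcomes section is short. It opens with "Adverse events were monitored" and gives no source, schedule or grading. It then defines the non-serious event: "an adverse event was considered as one requiring more than two additional opioid prescriptions within two weeks of discharge and/or access of confidential information by" an unauthorized person. The serious event follows: "We considered a serious adverse event as all-cause mortality and/or re-hospitalization for any reason".

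The same section lists two kinds of secondary outcome that bear on under-treatment: "supplementary opioid prescriptions within four weeks after discharge" and "pain intensity scores during the four weeks after discharge, and pain interference scores during the four weeks after discharge". Statistical analysis compares the first by logistic regression and the pain T-scores by linear mixed models, each by app group. It contains no analysis of adverse events. It does give, among its reasons for planning no interim analysis, that "the interventions were generally considered not harmful".

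Procedures describes what the app teaches, including "2) pharmacologic alternatives to opioids, 3) opioid safety and appropriate disposal". It also describes weekly notifications to participants, "reminding them to complete standardized surveys and custom questionnaires during the first four weeks following discharge", with telephone follow-up when nothing comes back through the app.

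**The concern.** The app aims to lower opioid intake and teaches patients about other analgesics. Three kinds of harm are foreseeable: pain that is not controlled, adverse effects of the opioids still taken, and adverse effects of the alternatives. The protocol treats the drug risks as relevant, since it excludes people with contraindications to opioids, acetaminophen or anti-inflammatory agents. Yet the non-serious definition names no drug effect and no unplanned care. Its only clinical criterion is a count of extra opioid prescriptions, over half the period used for the outcomes, and it shares a category with a data-privacy incident.

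What is at stake is the reading of the result. If opioid use falls in the app arm, the next question is whether patients paid for it. The belief that the interventions are not harmful cannot be tested with an event definition that leaves out most of the harms in question.

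**Working it through.** The documents state no adverse-event rate, safety margin or safety power, so there is no safety figure to reproduce. The check is to apply the stated rule to plausible events, illustrate the threshold, and look at the serious-event category.

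**Step 1: apply the definitions.**

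| Event after discharge | Non-serious event? | Serious event? | Captured elsewhere in the plan? |
|---|---|---|---|
| More pain, no extra prescription, no visit | No | No | Yes, PROMIS scores, mixed model |
| Two extra opioid prescriptions in week 1 | No, three are needed | No | Yes, four-week secondary outcome |
| Three extra opioid prescriptions in weeks 3 to 4 | No, outside two weeks | No | Yes, four-week secondary outcome |
| Emergency visit for pain, over-sedation or a bleed, treated and released | No | No | Nothing stated |
| Analgesic side effect managed at home | No | No | Nothing stated |
| Privacy breach | Yes | No | Not applicable |

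The first three rows are not classed as adverse events, but they are measured and compared by arm. The fourth and fifth rows are the gap: neither definition covers them and no outcome is stated for them. The fourth row's pain or prescriptions may show in the secondary outcomes, but the visit itself and any drug harm would not.

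**Step 2: how often the prescription threshold would be met.** The documents give no rate of extra prescriptions, so the rates here are assumptions. Let p be the proportion with at least one extra prescription in two weeks, and take 600 participants (300 per app group, from Sample Size Justification, times 2).

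- Poisson: m = −ln(1 − p), and P(X ≥ 3) = 1 − (1 − p)(1 + m + m²/2).
  - p = 0.10: m = 0.105, P = 0.00018, and 600 × P = 0.11.
  - p = 0.20: m = 0.223, P = 0.00157, and 600 × P = 0.94.
- Negative binomial with size 0.5 (strong clustering), matched on P(X ≥ 1) = p, so q = (1 − p)² and P(X ≥ 3) = 1 − (1 − p)[1 + 0.5(1 − q) + 0.375(1 − q)²].
  - p = 0.10: q = 0.81, P = 0.00232, and 600 × P = 1.4.
  - p = 0.20: q = 0.64, P = 0.01712, and 600 × P = 10.3.

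The numbers with any extra prescription are 60 and 120. The largest share reaching the threshold is 10.3/120 = 8.6%, so at these rates about 91% or more of people needing extra opioids would not be adverse events. Over a wider range of p, from 0.05 to 0.30, the share reaching it runs from about 0.04% (Poisson, p = 0.05) to about 18% (clustered, p = 0.30).

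This shows only that the clinical arm of the definition would rarely be triggered. People below the threshold still count in the secondary outcome. It says nothing about how often side effects or treat-and-release visits occur, and the documents offer no basis for estimating that.

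**Step 3: the serious-event category.** Study design and participants excludes people re-hospitalized within 30 days. Outcomes counts re-hospitalization for any reason as serious. If the exclusion refers to readmission after the index discharge and is applied after randomization, it would remove the events meant to show serious harm. If it refers to the admission at which people are enrolled, there is no conflict. The text does not say which. The modified intention-to-treat set, which drops people who did not use the app or left surveys unanswered, could remove more if safety were summarized in it.

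**The case against.** A reader might infer that under-treated pain goes unrecorded. The documents do not support that. Pain intensity and interference are secondary outcomes with weekly survey prompts and telephone back-up, the mixed model has categorical time, and the sample-size section gives a detectable difference for week-one pain intensity. Any supplementary prescription over four weeks counts, with no threshold of three. For pain, these are arguably more informative than an event tally.

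A reader might also infer that the safety comparison is built to look clean. That fails too: no adverse-event comparison by arm is planned and no safety conclusion is announced, while the serious category, covering death and readmission from any cause, is broad.

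Three further points are fair. The custom questionnaires are not reproduced and might ask about side effects. People with contraindications to the main analgesics are excluded, which lowers the risk. The randomized contrast is an educational app against a data-collection app.

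All of this narrows the point without removing it. The pain models estimate mean differences between arms; they do not count patients harmed and they carry no information on drug toxicity. Even if a questionnaire did collect side effects, the stated rule would not class them as adverse events and no analysis of them is described. A lower expected risk is not a reason to define events so that it cannot be checked.

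**Conclusion.** The point holds in a limited form. Analgesic side effects, and unscheduled or emergency visits without admission, fall outside both event definitions, and no adverse-event analysis by arm is specified. Few adverse events would therefore be uninformative about these harms and could not support a statement that the app is safe. Uncontrolled pain is covered, on average, by the secondary outcomes, so the gap concerns drug effects and unplanned care.

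Its size cannot be stated from the documents. The figures of about 0.1 to 10 people out of 600 describe only the prescription threshold, and rest on an assumed 10% to 20% with any extra prescription in two weeks and on assumed count distributions. Whether serious events are fully retained depends on how the 30-day exclusion is read. The primary opioid-use analysis is unaffected. This is a cheap improvement rather than a flaw that undermines the trial.

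**What to change.** 1. Widen the non-serious definition in Outcomes to include patient-reported or recorded adverse effects of opioid and non-opioid analgesics, and unscheduled or emergency visits for pain, over the same four weeks as the outcomes.
2. Collect these with one or two items in the existing weekly questionnaire and telephone follow-up, or state that the custom questionnaires already do so.
3. Add to Statistical analysis a summary of these events and of serious events by app arm, among all randomized participants. Keep supplementary prescriptions as the secondary outcome they already are.
4. List confidentiality breaches separately, as study-conduct incidents.
5. Reconcile the exclusion of people re-hospitalized within 30 days with the serious-event definition, stating which admission is meant and whether the exclusion applies after randomization.

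The cost is protocol wording, a slightly longer survey and more events to list; no extra visits, staff or participants are needed. The document is written in the past tense. If collection has closed, the survey items can no longer be added; recorded visits could be retrieved where linkage to the health record still allows, and the limitation should be stated with the results.

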Efficiency and Quality In Post- Surgical Pain Therapy After Discharge- EQUIPPED

NCT05221866

January 25, 2022

Methods

This trial was conducted at a Midwestern academic medical center and community hospital using a modified 2-by-2 randomized factorial design in which participants who underwent major inpatient surgery were randomly assigned to use a participant-facing consumer health informatics phone-based app with education versus an app for data collection only. Secondarily, a clinician-facing real-time opioid prescription decision support tool embedded into electronic health records was activated halfway through enrollment. The study design followed Pragmatic Explanatory Continuum Indicator Summary guidelines to maximize broad applicability and is reported according to Consolidated Standards of Reporting Trials Extension for Factorial Randomized Trials guidelines (Supplemental Digital Content 1).

Study design and participants

Participants were eligible for enrollment if they were 19-89 years old, had access to a smartphone, and had inpatient surgery requiring at least an overnight hospitalization with anticipated discharge to home. Individuals re-hospitalized within 30 days, pregnant, unable to read the English language, discharged to a post-acute care facility, with contraindications to opioids, acetaminophen, or nonsteroidal anti-inflammatory agents, or meeting the Agency for Healthcare Research and Quality (AHRQ) definition of long-term opioid therapy (opioid use on most days > 3 months) prior to surgery were excluded. All study data were deidentified.

Randomization and masking

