Participants were randomized 1:1 to the consumer health informatics smartphone-based intervention app or a control app with only data collection. Permuted block randomization (pairs) was performed using a computer-generated code within a secure central online data management system, Research Electronic Data Capture (REDCap), which was used to store and manage all participant data. No randomization was instituted for the clinician-facing intervention; instead, the decision support tool was embedded into the electronic health record to facilitate optimized opioid prescription upon discharge based on recorded inpatient use. This was implemented after half of the participants were enrolled. The principal investigator, coinvestigators, clinical coordinating center staff, participants, and statisticians remained masked to treatment assignment until the database was locked for analysis.

Sample Size Justification

To estimate power and sample size for the primary outcome, self-reported cumulative opioid use in the four weeks after discharge, investigators combined data from previous observational studies on opiates taken at one week from discharge, where variability in opioid consumption is greatest, and summed across four weeks from discharge and then log-transformed values appropriately. Investigators utilized SAS Proc Power (version 15.2, SAS Institute Inc., Cary, NC, USA) software and specified significance level alpha = 0.05 two-tailed. Across decision support tool activation status and surgical subspecialties, 300 participants per app group provided 85% power to detect minimum effect sizes (ES) of 0.23 in opioids consumed at one week and of 0.245 in opioids consumed across four weeks. Data was similarly

combined for pain intensity scores from prior studies and could detect a minimum effect size of 0.244 in pain intensity t-score at week one following discharge. Within decision support tool type and across specialty (i.e., the three-way interaction among app, decision support tool, and time), 150 participants per group provided 85% power to detect minimum effect sizes of 0.35 in opioids consumed at one week, 0.35 in opioids consumed across four weeks, and 0.35 in pain intensity t-score at one week after discharge.

Procedures

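### The primary model contains app group only, although surgical subspecialty and pre-operative opioid use are collected: a cheap precision gain of undocumented size is left unused

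*Combined protocol and SAP*

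**What the plan says.** The Statistical analysis section gives the primary model as "log-transforming the outcome variable and then fitting a linear regression model with the app treatment group as the covariate", with the effect expressed as a ratio of geometric means. The other analyses stated for this outcome are a quantile regression for robustness to outliers and a model with an app-by-decision-support interaction. No covariate-adjusted analysis is described.

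The Outcomes section lists many independent variables. Among them: "Clinical characteristics included the primary surgical subspecialty for the requisite hospital stay", and health history items including "pre-operative opioid use, preoperative benzodiazepine use, preoperative gabapentinoid use, and preoperative antidepressant use". None of these enters a stated model. Baseline balance is assessed by absolute standardised difference with a threshold of 0.16, but nothing follows when a variable exceeds it.

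The Sample Size Justification pools over surgical mix: "Across decision support tool activation status and surgical subspecialties, 300 participants per app group provided 85% power", for effect sizes that include 0.245 in four-week opioid use at two-sided 0.05. Randomization and masking describes 1:1 allocation in blocks of two and names no stratification factor. Surgical mix is therefore used neither in the allocation nor in the analysis.

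**The concern.** If subspecialty or pre-operative opioid use predicts opioid consumption after discharge, the residual variance in an app-only model is larger than it need be, and so is the confidence interval for the ratio of geometric means. In a linear model on the log scale, adjusting for variables fixed before randomisation targets the same ratio, so precision could be gained without changing the primary question.

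A second issue is prespecification. The plan lists many baseline variables and an imbalance threshold, but no rule for using either. Unless a covariate set is fixed before unmasking, any adjusted result reported later is a post-hoc choice.

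The omission does not itself bias the app effect. The modified intention-to-treat exclusions can cause bias on their own, but that is a separate matter which covariates do not settle.

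**Working it through.** **Inputs from the documents:** 300 per app group, two-sided alpha 0.05, effect size d = 0.245 (all from Sample Size Justification). No SD is given, so d is read as a difference in SD units of the log outcome.

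**Assumed, because the documents do not give them:** R² of the covariates, the number of covariate terms k, the spread between subspecialties, the prevalence of pre-operative use, and the amounts of loss and missing data.

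**Formula.** Noncentral t with n per arm:
- degrees of freedom = 2n − 2 − k
- variance factor V = (1 − R²)(1 + k/(2n − k − 3))
- noncentrality = d·√(n/2)/√V

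**Step 1: the plan's own figure.** With n = 300, k = 0 and R² = 0, the noncentrality is 0.245 × √150 = 3.001 on 598 df, and power is 85.0%. The stated 85% reproduces without covariates.

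**Step 2: adjusted, k = 10.** For example, at R² = 0.10, V = 0.90 × (1 + 10/587) = 0.915. The noncentrality is 3.001/√0.915 = 3.136 on 588 df, and power is 87.9%. CI width (log scale) relative to unadjusted is √V.

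| R² (assumed) | Power, 300 per arm | CI width ratio | Detectable d at 85% power | Power, 270 per arm |
|---|---|---|---|---|
| unadjusted | 85.0% | 1 | 0.245 | 81.1% |
| 0 | 84.4% | 1.008 | 0.247 | 80.4% |
| 0.05 | 86.2% | 0.983 | 0.241 | 82.3% |
| 0.10 | 87.9% | 0.957 | 0.235 | 84.3% |
| 0.20 | 91.3% | 0.902 | 0.221 | 88.2% |

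The 270 column supposes a 10% loss, because the plan does not say whether 300 is before or after the modified intention-to-treat exclusions.

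**Step 3: downside.** If the covariates explain nothing, power is 84.7%, 84.4% or 84.1% with 5, 10 or 15 terms. Break-even R² is 0.008, 0.017 or 0.025 respectively.

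**Step 4: what such an R² requires.**
- Subspecialty means with SD s, in units of the within-group SD, give R² = s²/(1 + s²). For s = 0.25, 0.33 and 0.50 this is 0.059, 0.098 and 0.20. Smaller spreads of 0.10, 0.15 and 0.20 give 0.010, 0.022 and 0.038, with power at 10 terms of 84.7%, 85.2% and 85.8%.
- Pre-operative use as a yes/no variable with prevalence p and a 0.5 SD difference gives v = p(1 − p) × 0.25 and R² = v/(1 + v). For p = 5%, 10% and 20% this is 0.012, 0.022 and 0.039.

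Participants meeting the "definition of long-term opioid therapy (opioid use on most days > 3 months) prior to surgery were excluded", which may further limit what pre-operative use can explain. Subspecialty would have to carry most of any gain.

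**Step 5: missing covariates.** Dropping participants without a covariate cancels the gain once more than 3.3%, 8.3% or 18.3% are dropped, at R² 0.05, 0.10 or 0.20 (k = 10). With 10% dropped and R² 0.05, power is 82.3%, below the unadjusted 85.0%.

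**Step 6: simulation check.** 4,000 trials per setting, blocks of two, 10 assumed subspecialties plus binary pre-operative use (Monte Carlo SE about 0.006). Unadjusted against adjusted power was 0.839 vs 0.836, 0.850 vs 0.858, 0.847 vs 0.880 and 0.853 vs 0.912 at R² 0, 0.05, 0.10 and 0.20. The mean app estimates agreed within 0.001.

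**Step 7: which variables are safe.** Participants had already undergone surgery when assigned, so subspecialty and pre-operative use precede randomisation. That cannot be said of "total in-hospital opioid intake, pain score at discharge, and length of hospital stay": these are complete only at discharge, and the documents do not say when in the stay randomisation took place. The Procedures section ranks 24-hour pre-discharge intake as the strongest predictor among those considered, but it has the same timing problem, and the Outcomes section lists only total in-hospital intake.

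**The case against.** The strongest reply has four parts.

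- **The plan is internally consistent.** The power calculation and the primary model match, and an unadjusted comparison of randomised groups is valid. This stands, and is why the point is a recommended improvement rather than a defect.
- **No document shows that either variable predicts the outcome.** This also stands. A subspecialty spread of 0.25 SD is as large as the app effect the trial is designed to detect. At spreads of 0.10 to 0.20 SD, adjustment with 10 terms moves power by between −0.3 and +0.8 points. The gain may be negligible, but the loss is bounded at under one point.
- **The main remedy may no longer be available.** The text is in the past tense, reports that opioid outcomes had no partial responses, and says the team "remained masked to treatment assignment until the database was locked for analysis". That reads like a finished trial, although the document is dated January 25, 2022. The status cannot be settled from the documents, so the fix has to be conditional on it.
- **Missing covariates may be rare.** Subspecialty should be known for every surgical inpatient, and "Health history variables were obtained via surveys and electronic health records as necessary". That is reasonable. The missing-data losses in the working arise only if incomplete cases are dropped, which a one-line rule prevents.

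**Conclusion.** The point holds as a missed, inexpensive improvement. The app-only primary model is valid and delivers its stated power. Adjusting for subspecialty and pre-operative opioid use would probably narrow the interval for the same ratio of geometric means, by 1.7%, 4.3% or 9.8% at assumed R² of 0.05, 0.10 or 0.20 with 10 terms and 300 analysed per arm. The corresponding power gains over 85.0% are 1.2, 2.9 and 6.3 points, against a loss of about 0.6 points if the terms explain nothing.

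Confidence is medium. R², the number of subspecialties and the covariate missingness are all assumed, and the benefit as a primary analysis depends on the data still being masked.

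**What to change.** First confirm whether the data are still masked, and state when in the hospital stay randomisation takes place.

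**If still masked:**
- Specify the primary linear model on log cumulative MME with app group, surgical subspecialty (categories fixed in advance) and pre-operative opioid use (coding fixed in advance).
- Add a missing-covariate rule, either a missing-indicator category or single imputation blind to arm, so that nobody is dropped.
- Keep the app-only model as a sensitivity analysis.
- Decision-support period, defined by tool status at enrolment, may be added as a design factor, with little gain claimed. An assumed average shift of 0.15 SD, with half the participants in each period, gives R² = 0.0056 and power of 85.1%.
- Do not adjust for total in-hospital intake, discharge pain or length of stay unless they are fixed before randomisation, and do not let the balance check trigger adjustment.

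**If already unmasked:** keep the app-only model as primary and report the adjusted model as supplementary, labelled post hoc.

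**Cost.** If masked: a wording change, a fixed category list and a missing-covariate rule, with no new data. The worst case is about 0.3, 0.6 or 0.9 points of power for 5, 10 or 15 uninformative terms. If unmasked: one extra labelled analysis.

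### The primary model omits the randomisation block of two, so the standard error of the app ratio is mildly conservative if block partners are alike

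*Combined protocol and SAP*

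**What the plan says.** Under Randomization and masking: "Participants were randomized 1:1 to the consumer health informatics smartphone-based intervention app" or a control app, and "Permuted block randomization (pairs) was performed using a computer-generated code". No matching or stratification factor is named, so a pair is two participants who share a block. The same section says of the clinician-facing decision support tool: "This was implemented after half of the participants were enrolled".

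Under Statistical analysis, the primary model is specified as "log-transforming the outcome variable and then fitting a linear regression model with the app treatment group as the covariate", and "The treatment effects were estimated as ratio of geometric means". A further model adds an app-by-tool interaction. Neither model has a block term, and no randomisation-based test is described. The model for opioids prescribed at discharge has the same app-only form. Participants who did not engage or did not answer the survey are left out of the analysis.

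Sample Size Justification "specified significance level alpha = 0.05 two-tailed" and gives, for 300 participants per app group and 85% power, an effect size "of 0.245 in opioids consumed across four weeks".

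**The concern.** A 1:1 block of two always contains one intervention and one control participant. Anything the partners share adds equally to both arms and drops out of the difference. The app-only regression treats all participants as independent, so it leaves that shared variation in the residual and in the standard error.

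The documents describe one such shared factor. The tool was switched on partway through enrolment, so apart from blocks that straddle activation, both partners belong to the same period. The tool acts on discharge prescribing, which may affect both the discharge prescription and later opioid use. If the halves differ, the confidence interval for the primary ratio is somewhat wider than the design warrants. That matters most if the app result is close to null.

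**Working it through.** **Inputs.** From the documents: 300 per app group, effect size 0.245 (SD units, log four-week opioid use), two-sided alpha 0.05, blocks of two. Assumed: the within-block correlation rho, the difference between enrolment halves, and the share excluded from analysis.

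**1. The plan's own figure.** With independent groups, SE = sqrt(2/300) = 0.0816 SD. Power = Phi(0.245/0.0816 − 1.96) = 85.1% (85.0% with the noncentral t), and the minimum detectable effect is 0.2447. The stated 85% reproduces with no block term. (The one-week effect size of 0.23 gives only 80.4% by the same formula; nothing here depends on it.)

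**2. Effect of blocking on the variance.** With complete pairs, the true variance of the log ratio is (2·SD²/n)(1 − rho), while the app-only model reports 2·SD²/n. The reported SE is therefore too large by a factor 1/sqrt(1 − rho). The actual two-sided type I error is 2·[1 − Phi(1.96/sqrt(1 − rho))].

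**3. A range for rho from the documented mechanism.** If the two halves differ by d within-half SDs, the between-half variance is d²/4 and rho = (d²/4)/(1 + d²/4). For example, d = 0.35 gives 0.0306/1.0306 = 0.030. Power is by the normal approximation for 300 complete pairs at effect size 0.245.

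| Assumed d | rho | SE too wide by | Type I error, app-only | Power, app-only | Power, using block | Forgone |
|---|---|---|---|---|---|---|
| 0 | 0 | 0% | 5.0% | 85.1% | 85.1% | 0 |
| 0.2 | 0.010 | 0.5% | 4.9% | 85.2% | 85.4% | 0.2 points |
| 0.35 | 0.030 | 1.5% | 4.7% | 85.5% | 86.1% | 0.7 points (before rounding) |
| 0.5 | 0.059 | 3.1% | 4.3% | 85.8% | 87.1% | 1.3 points |

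A paired t test on 299 degrees of freedom takes about 0.1 point off the gain.

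**4. Broken blocks.** If a random share m of each arm is excluded, the factor becomes 1/sqrt(1 − rho(1 − m)). With an assumed m = 20%, the three excesses fall to 0.4%, 1.2% and 2.4%.

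**5. Form of the block term.** A fixed block effect uses only complete blocks. In simulation at rho 0.03 with 20% exclusions, its SE was about 0.100, against 0.091 for the app-only model, so it would lose precision. A random intercept keeps unpaired participants. When rho is near zero its variance is often estimated at the zero boundary. Simulations of 100,000 trials of 300 complete pairs, with rho from 0 to 0.03, gave type I error between 5.0% and 5.3% (Monte Carlo SE 0.07 point).

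**The case against.** The best defence is that these are small blocks, not matched pairs. Leaving the block out of a simple permuted-block trial is common and valid. The point estimate is unaffected, and the error is on the safe side when rho is zero or positive. That stands.

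Three stronger readings are tempting, and the documents support none of them.

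- *That the trial discards power it was planned to have.* The sample size is an independent-groups calculation that reproduces without pairing, and the app-only model never falls below 85% in the table. Only extra precision is forgone.
- *That the interval could be 5% to 12% too wide.* That needs rho of 0.10 to 0.20. Inverting the formula, d = 2·sqrt(rho/(1 − rho)), the halves would have to differ by 0.67 to 1.0 SD, or 2.7 to about 4 times the 0.245 effect the trial is powered for. According to Procedures, the tool ran only for participants who needed no opioids in the day before discharge, which dilutes its effect on a whole half. Clustering of site, specialty or case mix along enrolment order could add resemblance, but the documents do not describe any.
- *That the primary test is anti-conservative.* This would need negative rho (at −0.05 the SE is 2.4% too narrow and type I error 5.6%). Nothing in the documents suggests a mechanism for that.

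**Conclusion.** The concern holds as a minor point. The design blocks in twos, the primary model ignores the block, and its SE is mildly conservative to the extent that partners are alike. Under the one block-shared factor the documents describe, and assuming the halves differ by 0.2 to 0.5 SD, the SE is about 0.5% to 3% too wide and roughly 0.2 to 1.3 points of power are forgone with 300 complete pairs. Both figures shrink once exclusions break blocks. If rho is zero there is nothing to gain. No conclusion about the app would be invalid because of this omission.

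**What to change.** In Statistical analysis, add a random intercept for randomisation block to the log-MME model and to the discharge-prescription model, the latter because the tool acts on that outcome most directly. Make it random, not fixed, so that participants whose partner is excluded still contribute.

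This assumes the block number can be recovered from the REDCap randomisation list; the documents mention only a computer-generated code within REDCap. If it cannot, add decision-support period as a covariate, which recovers the part of the gain that the documents can account for. The section is written in the past tense; if the primary analysis is already fixed, report the block-adjusted model as a labelled sensitivity analysis.

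The cost is about one sentence of text and slightly more analysis work. The statistical downside is type I error of up to about 5.3% when rho is near zero, so slight conservatism may be exchanged for very slight liberality.
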